Study Title: The Effects of Respiratory Training on Voice

NCT #: NCT04710862

Document Title: Protocol Summary

Document Date: May 25, 2025

Participants were recruited from local physicians, speech-language pathologists, communication disorder clinics, and ClinicalTrials.gov. Participants were included if ages 18 or older, were in good general health per self-report other than the voice disorder, with normal pulmonary function, reported problems with their voice that had been present for 2 months or longer, were non-smokers, had English as their primary language to avoid potential linguistically-based differences in acoustic measures of voice, showed adequate corrected or uncorrected vision to read basic graphs and print as determined with visual screening, showed no organic or neurologic vocal fold pathology per laryngology exam performed and assessed by a laryngologist, were not currently receiving voice therapy, did not report a bilateral severe or profound level of hearing loss, had a diagnosis of muscle tension dysphonia, showed acoustic dysphonia (Cepstral/Spectral Index of Dysphonia) that exceeded normative values for the participant's age and sex, showed one or more patterns of supraglottic activity and presence of normal/complete vocal fold closure patterns during laryngoscopy examination, and showed evidence of speech breathing abnormalities relative to normative values. Prior to scheduling the first visit, general information about the study was provided during a telephone screening to determine basic eligibility status, with a copy of the consent form emailed or mailed to them for review before the first appointment.

Assessments

In the initial assessment visit, informed consent was obtained and an initial voice questionnaire was completed. For all participants, speech breathing behavior and voice acoustic recordings were obtained during a variety of speaking tasks that were repeatedly administered to determine performance at baseline, after the training phase, and at long-term follow-up timepoints. The primary testing and training phases took place over an 8-week period that included two pre-training assessment sessions in week 1 (baseline assessments), six training sessions held 1xweek (weeks 2 through 7), and two post-training assessment sessions in week 8. Assessment visits were approximately 2 hours, and training sessions were approximately one hour.

Laryngoscopy evaluation was completed in week 1 if not recently performed and with recording obtainable through participant's consent. In addition to the acoustic and speech breathing measurement described below, questionnaires were completed at each assessment timepoint including the Voice Handicap Index-10 and quantification of self-reported speaking effort on a visual analog scale. Participants were provided compensation for their time spent during all assessment but not training visits.

Acoustic recordings were obtained with a digital recording system simultaneously with speech breathing recordings. The Computerized Speech Lab (Pentax Medical) was subsequently used for all analyses of the acoustic data. To record and display respiratory signals, the respiratory InductoTrace system (Ambulatory Monitoring Inc)

was used, which included placement of transducer bands around the rib cage and abdomen to record volume changes associated with inspiration and expiration. Procedures for speech breathing calibration and measurement were based on well-established methods used clinically and in research. Participants performed calibration tasks while lung volume was measured with a digital spirometer, noseclip and mouthpiece. Subsequent recordings of the change in volume for the rib cage and abdomen during speech productions were measured while the participant read a passage aloud, providing estimated lung volume levels without the use of the spirometer. Participants returned for long-term assessments at 3 and 6-months post-training. After all short-term sessions were completed (weeks 1-8), control (sham) condition participants were subsequently offered the experimental condition (described below).

Training

Participants with muscle tension dysphonia were randomly assigned to one of two conditions: 1) respiratory lung volume training (RLVT) and 2) a control training (CT) condition involving a sham training device. For the RLVT condition, after the initial assessment sessions, training session 1 addressed instruction and training on appropriate speech breathing behavior, the rationale for targeting increased lung volume initiation and termination levels, and the targeted movements of the rib cage and abdomen. Training sessions 2 through 6 directly trained higher lung volume level targets during speech. Specifically, higher levels of lung volume initiation and termination were targeted to capitalize on non-muscular forces contributing to speech production. Increased frequency of breaths and reduced words per breath group were also incorporated into speech training. Training for RLVT included real-time visual biofeedback of lung volume levels in graphic form, with signals displayed on a large screen monitor and target levels for lung volume initiation and termination superimposed on the graphic display. This visual biofeedback was used to enhance motor learning of new speech breathing patterns. A hierarchical progression of gradually increasing length and complexity of speech was followed throughout training to facilitate skill acquisition and transfer of skills, while also incorporating spontaneous speech throughout training. A videorecording of one training session was performed for each participant using a digital video camcorder and tripod. This was later rated by a research team member who did not perform the training to determine fidelity of the training to specified protocol goals and stimuli.

The CT condition provided respiratory-like “training” that was not expected to improve speech breathing, and has been used as a control (sham) respiratory condition in prior studies. Expiratory muscle strength training (EMST) is among the most frequently studied respiratory treatments in studies addressing vocal outcomes and has been studied in people with voice disorders. A commercially available device (EMST 150;

Aspire Products) was purchased in modified form as a sham-EMST device which removed the internal spring device that offers expiratory resistance. Multiple studies involving general respiratory training have effectively implemented this device with the spring removed as a sham respiratory condition that allows for participant blinding. In the CT condition, participants performed multiple sets of 5 exhalations each through the non-resistive device following a full inspiration, with intervening rest periods between each exhalation and longer rest periods between each set. Number of sessions and time per session were identical for the CT and RLVT conditions, including pre-training and post-training assessment visits.

A home practice program with homework tracking sheets was completed throughout all six training sessions for both the RLVT and CT conditions to facilitate carryover of training and equalize home practice time between the two conditions. Additional explanation and speech stimuli for a continued home practice program was provided at the post-training assessment sessions after RLVT. Participants were encouraged to continue structured home practice including tasks associated with daily activities of living at least three times a week through the 6-month time period elapsing between training completion and the final long-term follow-up session.

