**Study Title:** The Effects of Respiratory Training on Voice

**NCT #:** NCT04710862

**Document Title:** Statistical Analysis Summary

**Document Date:** May 25, 2025

Distribution characteristics were determined for all outcome measures to derive descriptive statistics and to test for statistical modeling assumptions (SPSS version 27.0 software). Pre- to post-training group differences and within-participant differences at follow-up timepoints were determined using mixed linear models to account for the effects of group, assessment timepoint, and timepoint x group interactions as well as correlated (repeated) measurements. Post-hoc tests for within-group comparisons of the long-term follow-up timepoints in the Respiratory Lung Volume Training (RLVT) condition were performed using a Sidak correction. Non-parametric tests or data transformation techniques were implemented for any variables that did not show normal distributions. Pre-training (baseline) equivalence of mean values between the RLVT and control training (CT) groups was tested through t-tests for all outcome measures. An alpha level of .05 defined statistical significance, and two-tailed tests were used for all tests.

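### Does the week-8 home-practice material for RLVT, or the unstated rule for combining two assessment sessions, undermine the week-8 comparison?

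*Protocol*

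**What the plan says.** The Protocol (Assessments) schedules two assessment sessions in week 1, weekly training in weeks 2 to 7, and "two post-training assessment sessions in week 8". Recordings come from speaking tasks "that were repeatedly administered to determine performance at baseline, after the training phase, and at long-term follow-up timepoints", and "questionnaires were completed at each assessment timepoint". For follow-up it says only: "Participants returned for long-term assessments at 3 and 6-months post-training". The number of sessions at each of those later points is not given.

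On home practice, the Training section states: "A home practice program with homework tracking sheets was completed throughout all six training sessions for both the RLVT and CT conditions". For week 8 it adds: "Additional explanation and speech stimuli for a continued home practice program was provided at the post-training assessment sessions after RLVT". It does not say at which of the two sessions this happened, or where it fell relative to the recordings. The same section says that the arms had the same number and length of sessions.

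The SAP fits "mixed linear models to account for the effects of group, assessment timepoint, and timepoint x group interactions", allows for correlation among repeated measurements, and checks baseline equivalence by t-tests. It has no session term and no rule for reducing two sessions to one value.

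**The concern.** Week 8 is the only post-training comparison between groups that the SAP names. Follow-up differences are described as within participants, and CT participants could take up RLVT once the short-term sessions were over. Anything given to one arm only, at the visits that produce the week-8 outcome, therefore deserves a question. Fresh speech stimuli handed to RLVT participants just before they read aloud for the recording could favour that arm.

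The session question adds to this. If the material was given at the first week-8 visit, its influence on the analysed value depends on whether the first session, the second or their mean was used. A reader also cannot rebuild the baseline or week-8 values from the documents alone. Matching the number and length of sessions across arms does not answer either question, because it fixes neither content nor order.

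**Working it through.** The documents give no sample size, standard deviation or session-level data, so there is no planned figure to reproduce. The check is algebra plus a comparison of the texts.

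**Order at week 8.** Let d be any immediate shift that the material produces in RLVT, and let s be the share of the week-8 value recorded after the material was given. Then bias = d × s.

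- Material after the last recording: s = 0, bias = 0.
- Material between the two sessions: s = 0 if the first session is analysed, s = 0.5 for the mean (bias d/2), s = 1 if only the second is analysed (bias d).
- Material before every contributing recording: s = 1, bias = d.

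The documents give no value for d. With an assumed range of 0 to 0.2 SD, the bias is 0 to 0.1 SD at s = 0.5 and 0 to 0.2 SD at s = 1. The range includes zero, and its upper end has no support in the documents. By week 8 an RLVT participant had completed six sessions of about one hour. Five of these (sessions 2 to 6) directly trained lung-volume targets, and home practice ran alongside. Further explanation for continuing the same practice is a small addition to that.

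**No CT counterpart.** Three statements belong together:

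- The Protocol (Assessments) says that CT participants were offered RLVT after weeks 1 to 8.
- The Training section describes the material as supporting continued practice over the months to final follow-up.
- The SAP confines its post-hoc follow-up comparisons to RLVT.

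The material serves a phase that is analysed in RLVT, and the sham arm had no evident need for a sham continuation package.

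**Two sessions, one timepoint.** Suppose the two sessions are replicates with equal variance V and correlation r. One session has variance V. The mean of two has variance V(1 + r)/2. The ratio is 2/(1 + r):

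| r (assumed) | variance of one session ÷ variance of mean |
|---|---|
| .6 | 2/1.6 = 1.25 |
| .8 | 2/1.8 = 1.11 |
| .9 | 2/1.9 = 1.05 |

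The choice therefore moves precision by 5% to 25% in variance over this range. It does not move the expected difference between randomised arms, provided that the rule is the same in both and the material did not come between contributing recordings. If the sessions held different tasks, which is plausible for a varied battery in visits of about two hours, there is nothing to average and the ratio does not apply.

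**What an analyst would do.** The planned baseline t-tests need one value per participant, and the repeated factor that the SAP names is the timepoint. Both point to a single value per timepoint. Entering both sessions as separate records would also be acceptable, provided that the covariance structure recognises that two records from one week belong together; the SAP does say that the model handles correlated measurements.

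**The case for a change.** The best case for acting is that both gaps are real, are not explained by redaction or text extraction, and would take only a sentence each to close. The Protocol refers to the post-training sessions in the plural. If material was handed out at both, some of it preceded the second visit and any recordings made there. The value that entered the model is basic information, and short documents are no excuse for leaving it out. The session question also remains even if the order was harmless.

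The factual part of this stands: a reader cannot tell from the documents which rule was used or when the material was given. The step from there to a defect does not. The plural may simply describe visits across participants, and no statement puts the material ahead of a recording. A sensitivity analysis restricted to recordings made before the material would rest on an event that has not been established. If some material did come early, it was RLVT content, so the contrast would include slightly more of the RLVT package. That is a question of timing more than a clear bias.

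**Conclusion.** No change to the plan follows. These are two gaps in brief, retrospective summaries, and ordinary practice fills both: hand out continuation material once measurements are finished, and form each timepoint value in the same way in both arms. Under those two assumptions the bias is zero and the only consequence is precision, 5% to 25% in variance if r lies between .6 and .9 and the sessions are replicates.

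Three limits apply to this conclusion. The effect and correlation ranges are assumptions, since the documents supply neither. Two sessions per timepoint are documented for weeks 1 and 8 only. The documents designate no primary outcome, so the point cannot be said to threaten one. If it emerged that material had preceded recordings in RLVT, the size of d would become a fair question for interpretation, but the documents give no ground for supposing so.

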**Study Title:** The Effects of Respiratory Training on Voice

**NCT #:** NCT04710862

**Document Title:** Statistical Analysis Summary

**Document Date:** May 25, 2025

Distribution characteristics were determined for all outcome measures to derive descriptive statistics and to test for statistical modeling assumptions (SPSS version 27.0 software). Pre- to post-training group differences and within-participant differences at follow-up timepoints were determined using mixed linear models to account for the effects of group, assessment timepoint, and timepoint x group interactions as well as correlated (repeated) measurements. Post-hoc tests for within-group comparisons of the long-term follow-up timepoints in the Respiratory Lung Volume Training (RLVT) condition were performed using a Sidak correction. Non-parametric tests or data transformation techniques were implemented for any variables that did not show normal distributions. Pre-training (baseline) equivalence of mean values between the RLVT and control training (CT) groups was tested through t-tests for all outcome measures. An alpha level of .05 defined statistical significance, and two-tailed tests were used for all tests.

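### The randomised pre-training to week-8 comparison is, as described, a difference in raw change scores: valid, but usually less precise than one adjusted for the baseline already collected

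*SAP*

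**What the plan says.** The Statistical Analysis Summary (SAP) bases the pre- to post-training comparison of the arms on "mixed linear models to account for the effects of group, assessment timepoint, and timepoint x group interactions", with allowance for repeated measurements. Pre-training is therefore one level of the time factor, and the arms may have different means there. The only other stated use of baseline is a check between arms: "Pre-training (baseline) equivalence of mean values between the RLVT and control training (CT) groups was tested through t-tests for all outcome measures". Some outcomes may leave this model altogether: "Non-parametric tests or data transformation techniques were implemented for any variables that did not show normal distributions".

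Three points in the Protocol Summary matter here.

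- Allocation is random (Training): "Participants with muscle tension dysphonia were randomly assigned to one of two conditions".
- After the week-8 assessments (Assessments), "control (sham) condition participants were subsequently offered the experimental condition".
- Entry depends on baseline severity (opening paragraph on eligibility): participants "showed acoustic dysphonia (Cepstral/Spectral Index of Dysphonia) that exceeded normative values" and also "showed evidence of speech breathing abnormalities relative to normative values".

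Baseline and post-training each comprise two assessment sessions. The SAP does not say how the two enter the model.

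**The concern.** Because the arms are randomised, any difference between their baseline means is chance. A model that gives each arm its own free baseline mean subtracts that chance difference in full. Adjustment removes only the part that predicts the week-8 value. Full subtraction is right only when a one-unit difference at baseline predicts a one-unit difference at week 8. Otherwise it adds noise.

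Control participants can move to RLVT after week 8, so pre-training to week 8 is the only clean randomised comparison in the trial. An avoidably wide interval there cannot be made good by the 3- and 6-month visits.

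**Working it through.** **Inputs.** From the documents: the model terms, random allocation, and two-sided alpha of 0.05. Not in the documents, so assumed: 1:1 allocation, n per arm, pre-post correlation ρ, and k = post-training SD / baseline SD. The documents state no precision or power figure to reproduce.

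**Step 1: what the planned contrast is.** In 500 simulated datasets (20 per arm, complete data, REML, unstructured covariance), the interaction contrast matched the difference in mean change to within 5e-15. In one dataset with ρ = 0.6 and a random intercept, both gave 0.8377 (SE 0.2068), and adding a follow-up visit for RLVT only left the estimate unchanged. The baseline-adjusted SE on the same data was 0.1902. With missing visits the equality is only approximate.

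**Step 2: large-sample variances.** Set the post-training SD to 1 and the baseline SD to 1/k. In units of 2/n:

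- change score: 1 + 1/k² − 2ρ/k
- baseline-adjusted: 1 − ρ²
- ratio, planned over adjusted: (1 + k² − 2ρk) / [k²(1 − ρ²)]

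The numerator minus the denominator is (1 − ρk)², so the ratio is never below 1. It equals 1 only when ρk, the slope of the week-8 value on baseline, is 1.

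| k | ρ 0.3 | ρ 0.5 | ρ 0.7 | ρ 0.9 |
|---|---|---|---|---|
| 1/1.2 | 1.89 | 1.65 | 1.49 | 1.47 |
| 1 | 1.54 | 1.33 | 1.18 | 1.05 |
| 1.2 | 1.31 | 1.15 | 1.03 | 1.02 |

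**Step 3: a small trial (assumed 20 per arm, ρ = 0.5).** The change score has 2n − 2 = 38 df. The adjusted analysis has 2n − 3 = 37 df, and its variance is multiplied by 1 + 1/(2n − 4) = 1 + 1/36 for estimating the slope. With k = 1:

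- planned half-width: 2.024 × √(0.1 × 1.00) = 0.64
- adjusted half-width: 2.026 × √(0.1 × 0.75 × 37/36) = 0.56

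| k | Half-width, planned v adjusted (post SDs) | Planned wider by | Power for an assumed 0.6 SD effect |
|---|---|---|---|
| 1/1.2 | 0.71 v 0.56 | 27% | 38% v 56% |
| 1 | 0.64 v 0.56 | 14% | 46% v 56% |
| 1.2 | 0.59 v 0.56 | 6% | 51% v 56% |

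Simulated variance ratios at 20 per arm and ρ = 0.5 (20,000 trials per cell) were 1.59, 1.31 and 1.12 in the same order. Mean estimates were 0.596 to 0.603 for a true 0.60, so neither method is biased.

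**Step 4: entry selection.** Selecting on the acoustic index and on speech breathing can shrink the baseline SD of those outcomes. This lowers ρ but raises k. Take a bivariate normal with equal SDs, cut at the mean of the analysed baseline, and unselected ρ = 0.5. Baseline variance falls to 1 − 2/π = 0.363, the covariance to 0.182, and post variance to 1 − 0.25 × 0.637 = 0.841. Within the trial ρ is 0.33 and k is 1.52. The change variance is 0.363 + 0.841 − 2 × 0.182 = 0.841 (from unrounded values), the adjusted variance is still 0.75, and the ratio is 1.12 rather than 1.33.

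| Cut applied to | Unselected ρ 0.3 | 0.5 | 0.7 |
|---|---|---|---|
| Analysed baseline value: variance ratio | 1.20 | 1.12 | 1.06 |
| Analysed baseline value: planned interval wider by, 20 per arm | 8% | 4% | 2% |
| Separate measurement correlated 0.8 with it: variance ratio | 1.37 | 1.28 | 1.21 |
| Separate measurement: planned interval wider by, 20 per arm | 15% | 11% | 9% |

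**Step 5: where the gain vanishes.** With k = 1 the adjusted interval is no narrower from ρ of about 0.87, 0.92 and 0.94 at 10, 15 and 20 per arm. With k = 1.2 at 20 per arm it is no narrower for ρ between 0.71 and 0.91, but at worst about 1.5% wider.

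**Step 6: averaging the two sessions.** If the sessions are averaged, with an assumed session correlation of 0.8 and k = 1, ρ = 0.5 becomes 0.5/0.9 = 0.56. The ratio is then 2/1.56, or 1.29 before rounding ρ.

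**Step 7: the baseline t-tests.** The largest non-significant gap is t(0.975, 2n − 2) × √(2/n): 0.75, 0.64 and 0.52 SD at 15, 20 and 30 per arm. A non-significant test therefore does not show equivalence.

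**The case against.** The planned model is a standard, valid analysis of a randomised pre/post trial, and nothing in it is an error. The SAP is a single paragraph, so a covariate may have been used and not mentioned. Both documents are in the past tense, so the analyses may already be done and an adjusted estimate would carry only post hoc weight. Every magnitude rests on assumed inputs. The wider gains ignore entry selection, which can cut them to a few per cent for the selected outcomes. The common-baseline model can also look better than it is. In the simulation its mean model SE was 0.267 against an empirical SD of 0.281, about 5% too small, while the covariate version gave 0.274 against 0.281.

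Most of this stands as a limit on size and weight. The point concerns precision only, is confined to the model as described, and does not reach outcomes analysed non-parametrically. It does not remove the recommendation. The possible loss from adjusting at 20 per arm is at most about 1.5% of interval width in the k = 1.2 case, while the possible gain is material, and the baseline data are already in hand. The SE shortfall is a reason to prefer the covariate version or to apply a small-sample correction.

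**Conclusion.** The concern holds. As described, and with complete data, the pre-training to week-8 contrast is a raw change-score difference. It is unbiased, but in large samples it is never more precise than a baseline-adjusted contrast.

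The gain cannot be fixed from the documents. Over the assumed grid (ρ 0.3 to 0.9, k 1/1.2 to 1.2) the variance factor runs from 1.02 to 1.89. For outcomes used to select participants it may be as low as 1.06, and in a very small trial with high ρ the gain disappears. The change should be made for the sake of precision. It is not needed for validity.

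The baseline t-tests are a secondary matter of wording and alter no treatment estimate.

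**What to change.** For each outcome analysed by the linear model, on its original or transformed scale, report the week-8 RLVT minus CT difference with its 95% interval, adjusted for that outcome's baseline on the same scale. Name one method:

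- **(a)** regress the week-8 value on arm and baseline; or
- **(b)** fit a mixed model with a common baseline mean, using an indicator that is 0 for everyone at baseline and 1 for RLVT at post-training, with unstructured covariance and a small-sample correction.

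Deleting the group main effect while keeping the interaction does not achieve (b). It refits the planned model, and in simulation the contrast was the same to 1e-14. With complete data (a) and (b) give the same estimate (agreement to 1.2e-7). Method (b) also keeps participants with no week-8 value. State how the two sessions at each timepoint enter the analysis.

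If results are already known, present the adjusted estimate as a labelled post hoc sensitivity analysis beside the planned contrast. Separately, replace the baseline t-tests with means and SDs by arm.

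The cost is a sentence in the SAP, one covariate or recoded indicator, and about one degree of freedom per outcome. No new data are needed.

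### As worded, the normality rule tests the outcome variable rather than the mixed model's residuals, so an outcome can leave an adequate original-scale model and the baseline-to-week-8 contrast

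*SAP*

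**What the plan says.** The SAP is a one-paragraph summary in the past tense. It opens by saying that "Distribution characteristics were determined for all outcome measures to derive descriptive statistics and to test for statistical modeling assumptions". The main analysis is a mixed linear model with group, assessment timepoint and "timepoint x group interactions as well as correlated (repeated) measurements". The rule at issue follows: "Non-parametric tests or data transformation techniques were implemented for any variables that did not show normal distributions". Neither document mentions residuals or random effects.

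Three facts in the Protocol bear on the rule.

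- The eligibility paragraph requires that participants "showed acoustic dysphonia (Cepstral/Spectral Index of Dysphonia) that exceeded normative values" for their age and sex, and that they "showed evidence of speech breathing abnormalities relative to normative values".
- Under Assessments, baseline comprises two sessions in week 1 and the post-training assessment two sessions in week 8. Also, "questionnaires were completed at each assessment timepoint including the Voice Handicap Index-10"; no entry threshold is stated for that index or for speaking effort.
- After the week 1 to 8 sessions, "control (sham) condition participants were subsequently offered the experimental condition". The randomised comparison is therefore baseline to week 8.

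**The concern.** A linear mixed model does not require the outcome itself to be normally distributed. If people enter only when a measure exceeds a cut-off, the raw baseline of that measure can be skewed while the residuals for pre-to-post change remain close to normal. A rule that tests the variable can then fire although the model is sound.

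Where the outcome goes next also matters. A Mann-Whitney test on change keeps the randomised baseline-to-week-8 contrast. A Mann-Whitney test at week 8 alone still compares the randomised groups but discards baseline, so it is not the timepoint-by-group test. Separate within-arm tests do not compare the groups at all. A transformation can stay within the mixed model, but it redefines the interaction. The wording allows any of these. At stake are some power and a clear statement of which contrast was tested.

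**Working it through.** **Inputs.** From the SAP: alpha .05, two-tailed. The documents give no sample size, correlation, effect size, cut-off position, normality test or transformation, so there is no planned figure to reproduce. Everything below is assumed: 20 per arm, session-to-session correlation r = .8, effect .5 population SD, Shapiro-Wilk at .05 on the raw baseline as the trigger, and half the population passing the entry cut-off.

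**Model.** Session score = true score (variance r) + error (variance 1 − r), both normal, with complete data. The timepoint-by-group test then equals the t-test on change. There were 4,000 simulated trials per cell. Mann-Whitney is abbreviated MW.

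| How entry relates to the analysed baseline | Raw baseline rejected | Power: change | Power: MW on change | Power: MW at week 8 only | Power: rule, week-8 fallback |
|---|---|---|---|---|---|
| One hard cut-off on the analysed value (extreme case) | 83.4% | 70.2% | 67.3% | 48.9% | 52.5% |
| Cut-off varies between people by .3 SD | 37.2% | 69.8% | 66.9% | 47.6% | 60.8% |
| Cut-off varies by .5 SD | 16.5% | 70.9% | 68.6% | 45.0% | 66.7% |
| Two sessions averaged | 32.0% | 93.7% | 92.6% | 57.5% | 82.7% |
| Two sessions averaged, cut-off varies by .3 SD | 19.0% | 93.6% | 92.0% | 55.5% | 86.8% |
| Separate screening value | 9.2% | 68.3% | 65.8% | 49.7% | 66.4% |

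Residuals for change were rejected in 4.3% to 5.4% of trials across the scenarios, so the model assumption holds while the raw-variable check fires in 9% to 83%.

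**Loss with a week-8-only fallback** (change power minus rule power), in row order: 70.2 − 52.5 = 17.7; 69.8 − 60.8 = 9.0; 70.9 − 66.7 = 4.2; 93.7 − 82.7 = 11.0; 93.6 − 86.8 = 6.8; 68.3 − 66.4 = 1.9. That is about 2 to 18 points, or 2 to 11 without the extreme case.

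**Loss with MW on change.** Approximate loss = share of trials switched × power gap.

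- Extreme case: .834 × (70.2 − 67.3) = 2.4 points.
- Cut-off varying by .3 SD: .372 × 2.9 = 1.1.
- Cut-off varying by .5 SD: .165 × 2.3 = 0.4.
- Remaining three rows: .320 × 1.1 = 0.4; .190 × 1.6 = 0.3; .092 × 2.5 = 0.2.

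This is about 0 to 2 points.

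**Dependence on correlation.** Before selection, the variance of change is 2(1 − r). At r = .8 that is 0.4, against 1 for week 8 alone; at r = .5 the two are equal. The simulation agrees (2,500 trials per cell):

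- At r = .5, change versus week-8-only MW is 40.0% versus 37.9% with cut-off spread .3, and 32.2% versus 35.0% with separate screening. The week-8 test is slightly ahead in the second case.
- At r = .9, the same pairs are 93.6% versus 55.5% and 92.3% versus 59.6%.

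**False positives.** Any single fallback fixed in advance gave 4.4% to 5.6%. Taking the smallest of three p-values after the trigger fires gave 5.0% to 9.0%. That is an upper bound on a practice the SAP does not describe.

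**Scale.** With hypothetical means CT 30 to 20 and RLVT 20 to 10, the raw interaction is (10 − 20) − (20 − 30) = 0. On the log scale the ratio of ratios is (10/20)/(20/30) = 0.75. An unnamed transformation can thus change whether an interaction exists.

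**The case against.** The strongest reply is that the sentence is ordinary shorthand in a one-paragraph summary. The SAP says the distribution check served to test modelling assumptions, which may well have included residuals. This stands: the wording does not show that residuals were ignored, and the point concerns only the rule as written.

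A reader might also infer that the mixed model was replaced. The SAP does not say so. A transformation can stay within the model, and rank tests may have been used only for the baseline t-tests.

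A reader might infer that the speech-breathing outcomes are truncated by eligibility. The Protocol asks for evidence of abnormality but names no measure or cut-off, so truncation of a particular outcome does not follow. Only the acoustic index has a named criterion. Its threshold varies with age and sex, which softens any skew, as would averaging the two baseline sessions.

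Finally, the larger power losses need one particular fallback, the week-8-only rank test. The SAP does not name it, and its stated interest in pre- to post-training group differences points the other way. That too stands. Leaving the test, scale and contrast unnamed would, by itself, be only missing detail. What remains is that the stated trigger is the wrong object for a linear mixed model and that a better check is cheap.

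**Conclusion.** The concern holds in limited form, with minor to moderate severity. As worded, the rule can move an outcome, most plausibly the acoustic index, off an adequate original-scale model, and it does not tie the substitute to the baseline-to-week-8 between-group contrast. On the assumed inputs the usual cost is small; it becomes material only if the fallback ignores baseline and the correlation between sessions is high.

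The documents do not support a claim that any outcome was wrongly switched, that residuals went unchecked, or that the error rate was materially inflated. The sizes rest wholly on the assumed sample size, correlation, effect, cut-off and normality test. With 10 and 30 per arm and cut-off spread .3, for example, the loss under a week-8 fallback is 40.6 − 37.5 = 3.1 and 88.5 − 76.6 = 11.9 points.

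**What to change.** Because the summary describes completed work, the change belongs in the report.

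1. Give the original-scale mixed model with the timepoint-by-group term for every outcome.
2. Judge normality on that model's residuals.
3. Where residuals are clearly non-normal, add one named analysis of the same baseline-to-week-8 between-group contrast. This can be the mixed model on a named transformed scale, or a Mann-Whitney test on change with the Hodges-Lehmann estimate and 95% CI. List the outcomes affected, with the original-scale result beside each.

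The cost is a short table and minor extra analysis, with no new data. There are two drawbacks: a Mann-Whitney test on change uses only participants with both timepoints, and transformed results are not in the original units.
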